1.1 Background

Amblyopia is the most common cause of monocular visual impairment in children, estimated to affect as many as 3.6% of the childhood population.¹ The natural history of amblyopia is relatively unknown although it has been reported that visual acuity may deteriorate further without treatment.^{2,3}

Although occlusion or patching of the sound eye has been the mainstay for amblyopia therapy, alternative treatment such as pharmacological or optical penalization may be as effective.⁴⁻⁶ In a randomized, controlled clinical trial of 419 children, 3 years to less than 7 years old with moderate amblyopia, patching was compared to atropine.⁷ Although improvement with atropine was initially slower, both treatments produced similar improvement after 6 months.

Although both patching and atropine have been proven effective for treating amblyopia, neither treatment is without adverse side effects. Patching is associated with compliance difficulties, the need for continuous monitoring, and social stigma. Negative side effects observed in children treated with atropine include light sensitivity, facial flushing, and fever.⁷ In a randomized clinical trial comparing patching to atropine as a treatment for amblyopia, a questionnaire to assess the impact of patching and atropine treatment on the child and family indicated that both treatments were well tolerated overall, however, patching had lower compliance and higher social stigma than atropine.⁸

Another treatment option for amblyopia is Bangerter occlusion foils or filters. Bangerter foils were introduced in 1960 to provide graded reduction of image quality to the sound eye.⁹ The filters are available in graded densities designed to reduce visual acuity to a range of 20/25 to 20/300. Table 1 shows filter densities and corresponding levels to which normal visual acuity is degraded by the filter, according to the manufacturer. The filters are worn on the back surface of the spectacle lens in front of the sound eye. One advantage of Bangerter filters compared with patching is that the lower density filters are not readily apparent and therefore would be expected to increase patient compliance due to reduced social stigma. Another advantage of Bangerter filters is that there is no opportunity for skin irritation from bandage adhesive, a commonly-reported side effect of patching⁷. In addition, there is a theoretical advantage that Bangerter foils are less disruptive to binocular function during treatment compared with other modalities such as patching. Disadvantages of Bangerter foils are that glasses must always be worn during treatment, it is easy to peek around the glasses, the foils may not degrade visual acuity to the labeled level, and the foils become soiled and fade with time, thus losing their treatment effect if not replaced frequently. Also, the relative rate at which Bangerter filters improve acuity has not been directly compared with patching or atropine. Bangerter filters are often prescribed for longer periods than either patching or atropine.

Filter Density	Visual Acuities*
1.0	~20/20
0.8	~20/25
0.6	~20/30
0.4	~20/50
0.3	~20/70
0.2	~20/100
0.1	~20/200
<0.1	~20/300
Light Perception	Light Perception

*Visual acuity level to which normal visual acuity is labeled to be degraded by the filter.

Bangerter foils have been used mainly as secondary amblyopia therapy following patching or atropine to either further improve or maintain the visual gain. Iacobucci and associates¹⁰ treated 18

156 children with Bangerter foils who had been previously treated with patching. Children were
157 changed to Bangerter foils because of either non-compliance with patching (10 patients) or lack of
158 further improvement with patching (8 patients). At the time patching treatment had been prescribed,
159 children ranged in age from 2-8 years old and had amblyopic eye acuities ranging from 20/30 to
160 20/200, with most acuities (10 of 18) between 20/40 and 20/60. Patching treatment was continued
161 for a mean of 8.5 months. Bangerter foil treatment was initiated the same day patching was
162 discontinued, at which time children had amblyopic eye visual acuity ranging from 20/25 to 20/60,
163 with most having acuity of 20/30 (8 of 18). After treatment with Bangerter foils for a mean
164 duration of 8 months, two thirds of patients (12 of 18) obtained amblyopic eye acuity of 20/20 or
165 equal to that of the sound eye. Of the remaining 6 patients, 5 obtained amblyopic eye acuity of
166 20/25 or 20/30 or within a half-line of the sound eye.

167
168 Bangerter foils have been used as primary therapy for moderate amblyopia, although there are few
169 reports addressing their efficacy or effectiveness. As a primary treatment of amblyopia, Iacobucci
170 and associates¹⁰ used Bangerter foils to treat 15 children, 3 to 8 years old, with amblyopia of 20/30
171 to 20/60 for a mean duration of 9 months. Two-thirds of patients (10 of 15) obtained amblyopic eye
172 acuity of 20/20 or better or equal to that of the sound eye. Of the remaining 5 patients, 4 attained
173 amblyopic eye acuity of 20/25 or 20/30 or within a half-line of the sound eye.

174
175 There is little consensus as to which density Bangerter foil should be used initially when treating
176 amblyopia. The method by which clinicians determine the initial filter density varies. Polling the
177 clinicians on this study's planning committee indicated wide variability. Among the methods
178 reported were 1) using a fixed density filter for all patients, 2) basing the density on visual acuity of
179 the amblyopic eye, 3) using a Bangerter bar to increase filter density until the patient switches
180 fixation, and 4) using different density filters for different patients but in somewhat of an arbitrary
181 fashion based on the clinician's own previous clinical experience. Informal surveys administered
182 during PEDIG investigator meetings held during the 2006 American Academy of Ophthalmology
183 and the American Academy of Optometry annual meetings indicated that most clinicians use an
184 empirical, rather than a customized methodology, to determine the initial Bangerter filter. In all
185 cases, failure to improve was associated with the prescription of a more dense filter.

186
187 Bangerter filters may not degrade the visual acuity to the level labeled by the manufacturer, as
188 suggested by pilot studies. In one study conducted by PEDIG investigators on 9 patients (2
189 teenagers and 7 adults) with normal visual acuity in each eye, the visual acuity was retested with
190 Bangerter filters of 0.2, 0.1, and < 0.1 densities.¹¹ For the 0.2 filter used, which according to the
191 manufacturer's label should reduce visual acuity to 20/100, the mean visual acuity was only reduced
192 to 20/25. For both the 0.1 and <0.1 filters, which are designed to reduce visual acuity to 20/200 and
193 20/300 respectively, the mean visual acuity was only reduced to 20/50.¹¹ In contrast, another study
194 of 20 adults with normal visual acuity in each eye reported a mean visual acuity reduction to 20/63,
195 20/250, and 20/125 for the 0.2, 0.1, and <0.1 Bangerter filters respectively.¹²

196
197 We speculate that the differences in visual acuity with the Bangerter filters may be due to the fact
198 that similarly graded filters are not of uniform density.¹³ There appear to be small clear areas in
199 some filters, possibly allowing the patient to search for an area where they see best. If clear or
200 reduced density areas do exist, it is not known to what extent this would be expected to affect the
201 treatment benefit of Bangerter filters.

202
203 Few data are available comparing Bangerter foils with patching for the treatment of amblyopia.
204 Bonsall¹⁴ randomized 14 patients, 3 to 10 years old, with previously untreated
205 strabismic/anisometric amblyopia to either 6 hours of daily patching or full-time Bangerter foils.

206 Baseline amblyopic eye acuity was 20/30 to 20/400 for the patching group and 20/30 to 20/200 for
207 the Bangerter group. The Bangerter foil prescribed was the minimum density foil needed to elicit a
208 switch in fixation from the sound eye to the amblyopic eye. Visual acuity was measured every 6-8
209 weeks until the amblyopic eye visual acuity was equal to that of the sound eye, an improvement that
210 was achieved in 5 of the 14 at the time the study was stopped. The average time to achieve equal
211 vision between the amblyopic and sound eyes was about 4.5 months (142 days) for the foil group
212 versus about 9 months (272 days) for the patching group. Both forms of therapy were equally
213 tolerated. Despite good preliminary data, a large randomized clinical trial comparing the
214 effectiveness of Bangerter filters with patching for the treatment of amblyopia has yet to be
215 conducted.

216

217 **1.2 Study Objectives**

- 218 • Primary: To evaluate the non-inferiority of Bangerter filters to 2 hours of daily patching as a
219 primary treatment for moderate amblyopia (20/40 – 20/80) in children ages 3 to <10 years.
- 220 • Secondary:
 - 221 ○ To determine the time course of visual improvement with Bangerter filter treatment.
 - 222 ○ To compare patient quality of life, measured by a modified Amblyopia Treatment
223 Index, between patients treated with patching vs. Bangerter filters.
 - 224 ○ To determine whether the degree of blurring of sound eye visual acuity relative to
225 the amblyopic eye visual acuity predicts improvement in acuity.
 - 226 ○ To determine whether fixation preference is predictive of improvement in visual
227 acuity.

228

229 **1.3 Synopsis of Study Design**

230 Major eligibility criteria (see section 2.2 for a complete listing)

- 231 • Age 3 to < 10 years
- 232 • Amblyopia associated with strabismus, anisometropia, or both
- 233 • No ocular cause apparent for reduced visual acuity
- 234 • Visual acuity 20/40 – 20/80 (71 to 54 letters inclusive) in amblyopic eye
- 235 • Visual acuity 20/40 or better (≥ 69 letters) in sound eye
- 236 • Interocular difference ≥ 3 logMAR lines (≥ 15 letters)
- 237 • No amblyopia treatment other than spectacles in last 6 months
- 238 • Currently wearing spectacles
- 239 • Appropriate spectacles have been worn for 16 weeks prior to enrollment or visual acuity
240 documented to be stable
- 241 • No myopia > -6.00 D spherical equivalent in either eye
- 242 • Cycloplegic refraction within 6 months prior to enrollment

243

244 Treatment Groups

245 Patients will be randomized to two treatment groups:

- 246 • 2 hours daily patching of the sound eye plus one hour near activities while patching
- 247 • Bangerter filter worn on sound eye spectacle lens full time (0.3 for 20/40-20/63 and 0.2
248 for 20/80) plus at least one hour near activities

249

250 Sample Size

251 170 patients (85 per group) with moderate amblyopia (20/40 to 20/80)

252

[figure not shown]
253

254 Visit Schedule

[figure not shown]
- 255 • 6 weeks \pm 2 weeks
256 • 12 weeks \pm 2 weeks: Increase intensity of treatment if acuity not improved 1 line (5 letters) or
257 more from baseline (*see section 3.4.2*)
258 • 18 weeks \pm 2 weeks: Increase intensity of treatment if acuity not improved 2 lines (10 letters) or
259 more from baseline and intensity of treatment not increased at 12 week visit (*see section 3.4.3*)
260 • 24 weeks \pm 2 weeks: Primary outcome (masked exam)

[figure not shown]
261
262 Primary Analysis
263 The primary outcome assessment is visual acuity at 24 weeks for both the amblyopic and sound
264 eyes.
265
266 The primary analytic approach for the amblyopic eye acuity will involve construction of a one-sided
267 95% confidence interval to assess non-inferiority based on a treatment group comparison of
268 logMAR visual acuity scores adjusted for baseline visual acuity scores in an analysis of covariance
269 (ANCOVA) model.
270
271 Sound eye acuity data will be reported for each treatment regimen at the 24-week visit as mean
272 change from baseline and as the distribution of the numbers of lines of change from baseline.
273

274 **1.4 Study Summary Flow Chart**
 275

276

278
279
280
281

*Amblyopia resolved = Amblyopic eye acuity better than or equal to (<1 line or <5 letters) sound eye acuity

CHAPTER 2: PATIENT ENROLLMENT

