2.2 Eligibility and Exclusion Criteria

1. Age 3 to < 10 years
2. Amblyopia associated with strabismus (comitant or incomitant), anisometropia, or both
 - Criteria for strabismus: At least one of the following criteria must be met
 - Heterotropia at distance and/or near fixation on examination (with or without spectacles)
 - History of strabismus surgery (or botulinum)
 - Documented history of strabismus which is no longer present (and which, in the judgment of the investigator, is the cause of amblyopia)
 - Criteria for anisometropia: At least one of the following criteria must be met:
 - ≥ 0.50 D difference between eyes in spherical equivalent
 - ≥ 1.50 D difference between eyes in astigmatism in any meridian
3. Visual acuity, measured using the ATS single-surround HOTV protocol for patients aged < 7 years and the E-ETDRS protocol for patients 7 to < 10 years using the Electronic Visual Acuity Tester (the protocol for conducting the visual acuity testing is described in the *ATS Visual Acuity Testing Procedures Manual*), meeting the following criteria:
 - Best-corrected visual acuity in the amblyopic eye 20/40 to 20/80 inclusive (71 to 54 letters inclusive)
 - Best-corrected visual acuity in the sound eye $\geq 20/40$ (≥ 69 letters)
 - Inter-eye acuity difference ≥ 3 logMAR lines (i.e., amblyopic eye acuity at least 3 lines by ATS-HOTV or at least 15 letters by E-ETDRS worse than sound eye acuity)
4. No amblyopia treatment other than spectacles in the past 6 months.
 - Any treatment more than 6 months prior to enrollment is acceptable
5. Spectacles must be worn currently
6. Spectacle correction for measurement of enrollment VA must meet the following criteria and be based on a cycloplegic refraction (using cyclopentolate 1%) that is no more than 6 months prior to enrollment:
 - a. Requirements for spectacle correction:
 - Spherical equivalent must be within 0.50 D of fully correcting the anisometropia
 - Hypermetropia must not be undercorrected by more than +1.50 D spherical equivalent, and reduction in plus must be symmetric in the two eyes

- 327 • Cylinder power in both eyes must be within 0.50 D of fully correcting the
- 328 astigmatism
- 329 • Cylinder axis in the spectacle lenses in both eyes must be within 6 degrees of
- 330 the axis of the cycloplegic refraction when cylinder power is ≥ 1.00 D
- 331 • Myopia of the amblyopic eye greater than 0.50 D by spherical equivalent must

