4.5.2 Risk of Patching

The risks involved in the study are identical to those that would be present for a patient treated with occlusion therapy with patching who is not participating in the study.

In view of the small number of hours of daily patching, significant skin irritation is unlikely. If irritation occurs, the parent will be advised to put an emollient on the skin and discontinue use of the patch for a day.

Patching potentially could decrease the visual acuity in the sound eye, although this is almost always reversible. However, this occurrence is extremely unlikely in view of the small number of hours of daily patching. The diagnosis and management of reverse amblyopia is left to the investigator's judgment.

Patching could precipitate the development of an ocular deviation, although this has been found to be very rare in our previous studies and indistinguishable from the natural history of the condition. If treatment precipitates the development of an ocular deviation (e.g., esotropia in child with hyperopia), the parent will be advised to have the patient see the investigator as soon as possible.

669
670 There are some activities that should not be performed when patched due to the level of vision in
671 the amblyopic eye, such as riding a bike, in-line skating, skateboarding, or other activities in which
672 the patient could get hurt. The consent form will explicitly instruct parents not to allow their child
673 to perform such activities while patched.

674 **4.5.3 Risk of Bangerter Filters**

675 The risks involved in the study are identical to those that would be present for a patient treated with
676 Bangerter filters who is not participating in the study.

677
678
679 The more dense Bangerter filters potentially could decrease the visual acuity in the sound eye,
680 although this is almost always reversible. However, this occurrence has not been reported. The
681 diagnosis and management of reverse amblyopia is left to the investigator's judgment.

682
683 There are some activities that may require extra caution when using the Bangerter filter due to the
684 level of vision in the amblyopic eye and blurring in the sound eye. These activities include riding a
685 bike, in-line skating, and skateboarding. The consent form will instruct parents that the child may
686 require more supervision when performing these activities.

687 **4.6 Reporting of Adverse Events**

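### Sound-eye acuity is named in the primary outcome, but the protocol plans no between-arm estimate or interval for it, only change from baseline by regimen

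*Protocol*

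**What the plan says.** Protocol section 1.3, under Primary Analysis, defines the outcome for both eyes: "The primary outcome assessment is visual acuity at 24 weeks for both the amblyopic and sound" eyes. It then treats the two eyes differently.

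- **Amblyopic eye:** a one-sided "95% confidence interval to assess non-inferiority based on a treatment group comparison of" logMAR scores, adjusted for baseline by ANCOVA.
- **Sound eye:** "Sound eye acuity data will be reported for each treatment regimen at the 24-week visit as mean" "change from baseline and as the distribution of the numbers of lines of change from baseline".

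Section 5.2 repeats the ANCOVA and the 0.075 logMAR limit without naming an eye; section 1.3 ties that analysis to the amblyopic eye. No part of chapter 5 gives a sound-eye difference between arms, an interval or a threshold for loss. Section 5.3.3 uses sound-eye acuity through the filter, but as a predictor.

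The sound-eye baseline is also an entry reading. Section 2.2 requires 20/40 or better in that eye and "Inter-eye acuity difference ≥ 3 logMAR lines". Section 2.5.2 has one acuity test serve both eligibility and baseline, and section 2.4 allows discretionary retesting for eligibility.

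Section 4.5.2 recognises that patching could reduce sound-eye acuity. Section 4.5.3 says the same of filters: "The more dense Bangerter filters potentially could decrease the visual acuity in the sound eye".

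**The concern.** The sound eye is the eye that is covered or blurred, and its initial exposure differs greatly by arm: a full-time filter against 2 hours of patching a day. If one treatment costs the sound eye more than the other, the randomized contrast is where that would show.

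Change within one arm mixes several things:

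- any treatment effect;
- regression to the mean, because children whose sound eye happened to read well on the entry test pass the 3-line rule more easily;
- test-retest noise, which fills the tails of a lines-of-change table;
- growth and practice between ages 3 and 10, which push towards gain.

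There is no untreated arm against which to calibrate these. Randomization makes the last three equal in expectation between arms, so an adjusted between-arm difference removes them. The protocol uses that approach for the amblyopic eye and does not plan it for the other eye in the same outcome. At stake is how clearly a non-inferiority result for the amblyopic eye can be read beside its relative cost to the sound eye.

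**Working it through.** **1. The plan's own figure.** Section 5.1 uses a limit of 0.075, SD 0.16, correlation 0.20, one-sided 5% and 90% power.

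- Adjusted SD = 0.16 × √(1 − 0.20²) = 0.1568.
- Normal formula: n per arm = 2 × [0.1568 × (1.645 + 1.282) / 0.075]² = 74.8, so 75 per arm and 150 in all.
- The noncentral-t version with ANCOVA degrees of freedom gives 76 per arm, 152 in all (power 0.902), as stated.
- 152 / 0.9 = 169, and the plan has 170.

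The sample size reproduces, but it serves the amblyopic eye. No figure is given for the sound eye.

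**2. What the entry rule does to sound-eye change.** The documents give no sound-eye SD or test error, so these are assumptions: true sound-eye acuity N(0.05, 0.10) logMAR, true amblyopic-eye acuity N(0.42, 0.15), independent single-test error SD 0.04, 0.06 or 0.08, and no true change. Readings were simulated in whole lines (HOTV) or letters (E-ETDRS), selected on the section 2.2 limits, and the sound eye was retested. Positive change means apparent loss.

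| Method, error SD | Mean change with rule (logMAR) | ≥1-line loss, with rule | ≥1-line gain, with rule | ≥1-line loss, no rule |
|---|---|---|---|---|
| HOTV, 0.04 | 0.005 | 24% | 19% | 22% |
| HOTV, 0.06 | 0.010 | 32% | 25% | 29% |
| HOTV, 0.08 | 0.016 | 38% | 28% | 33% |
| E-ETDRS, 0.04 | 0.005 | 7% | 5% | 6% |
| E-ETDRS, 0.06 | 0.010 | 17% | 11% | 15% |
| E-ETDRS, 0.08 | 0.018 | 26% | 16% | 21% |

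At 5 letters per 0.1 logMAR, the largest mean shift here is 0.018 × 50 = 0.9 letters. The rule adds about 1 to 5 percentage points to apparent 1-line losses; the rest is noise that would appear without selection. Without the rule, losses and gains balance. With it, losses exceed gains. Apparent 2-line losses with the rule run from 0.05% to 12%.

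Varying the assumed true means (sound eye 0.00 to 0.10, amblyopic eye 0.40 to 0.45; letter scoring) gives mean shifts from 0.003 to 0.025 logMAR. The top of that range is 1.3 letters, when the sound eye averages 0.10 and the error SD is 0.08. Growth and practice were not modelled.

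**3. Precision of the missing contrast.** Half-width of a two-sided 95% CI = 1.96 × SD × √(2/76), with the SD assumed.

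- SD 0.08: 0.025 logMAR (1.3 letters).
- SD 0.10: 0.032 logMAR (1.6 letters).
- SD 0.12: 0.038 logMAR (1.9 letters).

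If the arms are truly equal, the chance that the interval excludes a 2-letter (0.04 logMAR) excess loss is Φ(0.04/SE − 1.96), with SE = SD × √(2/76). This is 87%, 69% and 54% for the three SDs.

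**4. The 2-line proportion.** If 5% in each arm lost 2 lines, the half-width for the difference would be 1.96 × √(2 × 0.05 × 0.95 / 76) = 6.9 percentage points. This is coarse, so the mean difference carries most of the information.

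**The case against.** The strongest reply is that the sound-eye sentence is a safety summary in a synopsis. Chapter 5 leaves detail to an analysis plan that will supersede section 5.2, and section 5.2 says the primary approach will be developed with the DSMC. That plan is not shown and may contain the comparison. This limits the point but does not remove it: section 1.3 does not leave the sound-eye method open. It fixes one, for something it calls primary, and that method is descriptive.

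Second, both randomized arms are tabulated on the same measures at the same visit, so the contrast can be formed by eye, and the distribution shows gains beside losses. This stands. A reader might infer that the planned tables cannot be interpreted at all, and the documents do not support that. What is missing is the baseline-adjusted difference and its precision.

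Third, a reader might take the apparent 1-line losses of up to 38% as the product of the entry rule. The comparison without the rule shows otherwise.

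Fourth, both arms treat the sound eye, and section 4.5 recognises possible loss in each. It is tempting to say that harm should be judged on the between-arm difference. That would be wrong, because harm common to both arms cancels there. Within-arm change, for all its weaknesses, is the only planned summary that could signal it.

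Finally, sound-eye problems are covered clinically elsewhere: acuity of each eye at every visit (3.4), work-up of worsening (4.3) and DSMC review of complications (4.6). These protect individual children but do not estimate a difference between treatments.

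**Conclusion.** The point holds in limited form. The protocol names sound-eye acuity in its primary outcome, then plans no between-arm estimate or interval for it, although randomized data would supply one at no cost in patients. Regression to the mean is a minor part of the argument: under one letter with the central assumptions, and at most 1.3 letters over the wider range tried. Retest noise explains most apparent 1-line losses. All these sizes rest on assumed SDs and acuity distributions.

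A reader might infer that the non-inferiority conclusion is at risk. It is not: the margin, the test and the sample size concern the amblyopic eye and are unaffected. Nor would the added contrast guarantee excluding a 2-letter excess loss; with equal arms the chance is 54% to 87% for SDs of 0.12 to 0.08. It measures the differential effect on the sound eye, not absolute harm.

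**What to change.** In sections 1.3 and 5.2, add for the sound eye:

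- the Bangerter-minus-patching difference in 24-week acuity, from an ANCOVA on baseline sound-eye acuity in the same form as for the amblyopic eye, with a two-sided 95% CI;
- the between-arm difference in the proportion losing 2 or more lines.

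Describe both as measures of differential sound-eye effect. Keep the planned within-arm mean change and lines-of-change tables, and do not state that harm is judged on the between-arm difference alone. If only description is intended, section 1.3 should instead label sound-eye acuity as a descriptive safety outcome and not as part of the primary outcome.

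The cost is a few lines of wording, one extra model and one extra comparison of proportions. Section 3.4.4 already has both eyes tested masked at 24 weeks, so no new data are needed.
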